**Table 1: Censoring/event scenarios (for ITT and PP analysis of confirmed platelet response)**

Case	Description	Time at risk/ Time to recovery of platelets (days)	Responder	Censored (No = 0; Yes = 1)
1	No event in 30 days of continuous daily PE a	30	No	1
2	At day 30, confirmed recovery of platelets (per protocol)	30	Yes	0

Case	Description	Time at risk/ Time to recovery of platelets (days)	Responder	Censored (No = 0; Yes = 1)
3	At day x b (1 st measurement of platelet recovery), confirmed recovery of platelets, ideal case (per protocol)	x	Yes	0
4	No event occurred and subject is no longer in trial at day x b (including replaced subjects who are dosed)	x	No	1
5	At day x b (1 st measurement of platelet recovery), subject has recovery of platelets, however, missing data at 48 hours later, and no subsequent confirmation on platelet count during daily PE (no more daily platelet measurements) c	x	No	1
6	No recovery of platelets, however, daily PE stopped (daily PE considered surrogate for response d ). Except if PE stopped due to AE e (then idem case 4)	Time of last daily PE	No	1
7	Subject not dosed (after randomisation)	1	No	1

a PE = plasma exchange.

b At day x within 30 days assessment period.

c No subsequent confirmation during daily PE, since daily PE has been stopped by Investigator for clinical response which does not meet protocol definition of response.

d Certain subject's platelet counts 'hover' around 150,000/ $\mu$ L, and in clinical practice, PE is stopped.

e Start and stop dates of adverse events related to PE will need to be compared to PE stop dates in order to identify PE stopped due to AE.

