4. TRIAL DESIGN

4.1 Study Endpoints

4.1.1 Primary Endpoint

- Time-to-response, based on the following criteria:
 - Recovery of platelets $\geq 150,000/\mu\text{L}$
 - This response must be confirmed at 48 hours after the initial reporting of platelet recovery equal to or above $150,000/\mu\text{L}$ by a *de novo* measure of platelets $\geq 150,000/\mu\text{L}$ and LDH $\leq 2 \times \text{ULN}$ (i.e. “confirmed platelet response”)

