7.5 Assignment to Treatment

Subjects will be assigned to one of the two treatments according to a computerised randomisation schedule. When the randomisation number and treatment assignment are obtained, the randomisation number will be recorded on the CRF. This is a single blinded study. The Investigator will be informed of the treatment at the time of randomisation.

Randomisation is performed via an interactive web-based system.

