- The neurocognitive battery, if NOT performed at baseline, will be administered once as soon as possible, i.e., when level of consciousness and attentiveness of the subject permits and environmental factors are appropriate to support neurocognitive testing (e.g., subject is able to sit upright and interact with computer touch screen; subjects have eyeglasses used for reading and hearing devices, if applicable; testing area is quiet and relatively free of distracting stimuli).
- The bleeding score according to the modified ITP bleeding score will be performed daily during daily PE period, on the first day after the daily PE period and then weekly for the subsequent time interval until the last day of study drug administration.
- Assessment of clinically relevant bleeding will be performed daily during daily PE period, on the first day after the daily PE period and then weekly for the subsequent time interval until the last day of study drug administration.
- 12-lead ECG daily during the hospitalisation if it was abnormal at baseline. In addition, an ECG will be taken on day 1 and day 4, 4-6 hours post-study drug even when ECG was normal at baseline. The ECG will also be performed at pre-discharge and weekly after discharge until the last day of study drug administration.

Sampling for local laboratory:

- Blood sampling for chemistry will include the following: glucose, AST, ALT, LDH, CRP, creatinine, urea (BUN), uric acid, protein, albumin, haptoglobin, Na, K, Ca, Mg and Cl (local laboratory). The blood sample will be drawn daily during daily PE period, on the first day after the daily PE period and then weekly until the last day of study drug administration.
- Blood sampling for haematology will include the following: haemoglobin, haematocrit, MCV, MCH, MCHC, full blood count including RBC, WBC, differential, reticulocytes, optical platelet count and immature platelet fraction (local laboratory). In case optical platelet counts are not available, they can be replaced by measurements based upon impedance. If not available in the local laboratory, immature platelet fraction measurements can be omitted; The blood sample will be drawn daily during daily PE period, on the first day after the daily PE period and then weekly until the last day of study drug administration.

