Haematology includes haemoglobin, haematocrit, MCV, MCH, MCHC, full blood count including RBC, WBC, differential, reticulocytes, optical platelet count and immature platelet fraction. Coagulation variables include fibrinogen, aPTT, PT, INR, vWF:Ag and FVIII (chromogene or alternative method).

8.1.4 **Unscheduled Additional Visit**

In case of unscheduled additional visits, the following assessments will be performed at a minimum (Table 13):

- Concomitant medication taken since the previous visit must be recorded on the Concomitant Medications page of the CRF. Concomitant medications initiated, stopped, up-titrated or down-titrated for an AE will also be recorded on a specific Concomitant Medications page of the CRF. Transfusion of RBC units will be recorded as concomitant medication
- Clinical assessment will include physical examination and vital signs (blood pressure and heart rate at rest, body temperature)
- Bleeding score according to the modified ITP bleeding score
- Assessment of clinically relevant bleeding
- AE recording
- 12-lead ECG
- Blood sampling for chemistry will include the following: glucose, AST, ALT, LDH, CRP, creatinine, urea (BUN), uric acid, protein, albumin, Na, K, Ca, Mg and Cl (local laboratory)
- Blood sampling for haematology will include the following: haemoglobin, haematocrit, MCV, MCH, MCHC, full blood count including RBC, WBC, differential, reticulocytes, optical platelet count and immature platelet fraction (local laboratory). In case optical platelet counts are not available, they can be replaced by measurements based upon impedance. If not available in the local laboratory, immature platelet fraction measurements can be omitted
- Blood sampling for coagulation variables will include: fibrinogen, aPTT, PT, INR, vWF:Ag and FVIII chromogene (local laboratory). In case FVIII chromogene is not available in the local laboratory, it can be replaced by an alternative method (e.g. one stage clotting assay)
- Blood sampling for markers for cardiac cell death: Troponin T (local laboratory). In case Troponin T is not available in the local laboratory, it can be replaced by Troponin I
- Blood sampling for markers for heart failure: BNP or NT-proBNP (local laboratory)
- Blood sampling for markers for brain damage: NSE, S β 100 (central laboratory)
- Blood sampling for PK and RICO, if applicable (additional visit during period of administration of study drug (central laboratory)

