Complete remission: Complete remission is defined as recovery of platelets (confirmed by platelets  $\geq 150,000/\mu\text{L}$  and LDH  $\leq 2 \times \text{ULN}$  at 48 hrs after initial platelet response) and absence of exacerbation.

Initial platelet recovery: Date of initial platelet recovery is defined as the first occurrence of platelets  $\geq 150,000/\mu\text{L}$  which is **confirmed** 48 hours later by platelets  $\geq 150,000/\mu\text{L}$  and LDH  $\leq 2 \times \text{ULN}$ . For example, if platelets reach  $\geq 150,000/\mu\text{L}$  on Day 5, are not confirmed at Day 7, reach  $\geq 150,000/\mu\text{L}$  again on Day 10 and are confirmed at Day 12, the initial platelet recovery occurs on Day 10. Initial platelet recovery and confirmation dates will be determined using the actual lab results, following standardisation to consistent units.

Time to Response: Time to response will be calculated as the number of days, hours and minutes (represented by number of days with two significant digits after the decimal point) from study drug administration to initial platelet recovery, as defined above. An

---

observation is censored if the observation does not meet the defined time interval of 30 days, due to any cause of loss-to follow-up (including death), or endpoint not being reached.

Subjects that attain confirmed platelet response:

Time-to-Response = [Date and time (hrs, min) of initial platelet recovery] – [Date and time (hrs, min) of first study drug administration]

Exacerbation: Exacerbation of TTP is defined as recurrent thrombocytopenia following a confirmed platelet response and requiring a re-initiation of daily PE treatment  $\geq 1$  day but  $\leq 30$  days after the last daily PE.

Relapse: Defined as de novo event of TTP that occurs later than 30 days after the last daily PE.

First PE: Defined as start of PE.

First on-study PE: Defined as first PE received after randomisation.

In case first on-study PE is not first PE, then first on-study PE should be started within 24 hours (after the end) of the first PE. If not it is considered major protocol deviation.

Overall duration of study treatment exposure (days): Defined as date of last dose of study treatment – date of first dose of study treatment + 1

Duration of study treatment exposure during daily PE (days): Defined as date of last dose of study treatment during the daily PE period – date of first dose of study treatment during the daily PE period + 1

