5	At day xb (1st measurement of platelet recovery), subject has recovery of platelets, however, missing data at 48 hours later, and no subsequent confirmation on platelet count during daily PE (no more daily platelet measurements)c	x	Yes	0
6	No recovery of platelets, however daily PE stopped (daily PE considered surrogate for responsed). Except if PE stopped due to AEe (then idem case 4)	Time of last daily PE	Yes	0
7	Subject not dosed (after randomisation)	1	No	1

a PE = plasma exchange.

b At day x within 30 days assessment period.

c No subsequent confirmation during daily PE, since daily PE has been stopped by Investigator for clinical response which does not meet protocol definition of response.

d Certain subject's platelet counts 'hover' around 150,000/ $\mu$ L and in clinical practice PE is stopped.

e Start and stop dates of adverse events related to PE will need to be compared to PE stop dates in order to identify PE stopped due to AE.

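### If the last daily PE falls on the day of first platelet recovery or the day before, no platelet/LDH sample is scheduled at 48 hours, and the primary analysis censors the unconfirmed subject at recovery

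*SAP*

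**What the plan says.** - **Endpoint.** Protocol 4.1.1: "This response must be confirmed at 48 hours after the initial reporting of platelet recovery equal to or above" the platelet threshold, by a new platelet count and an LDH of at most 2 × ULN. SAP 6.3.1 repeats this. Neither document gives a window around 48 hours.
- **Sampling.** Protocol 8.1.2, for local chemistry (LDH) and haematology (platelets): "The blood sample will be drawn daily during daily PE period, on the first day after the daily PE period and then weekly". Table 11 puts the daily samples before PE and gives the weekly ones ±2 days. It has no row for a confirmatory sample.
- **Other routes to a sample.** Protocol 8.1.4: "In case of unscheduled additional visits, the following assessments will be performed at a minimum", and the list that follows includes haematology and LDH. SAP section 3: "Initial platelet recovery and confirmation dates will be determined using the actual lab results", so an unscheduled result would count.
- **Coding.** SAP Table 1, case 5 covers recovery on day x with "missing data at 48 hours later, and no subsequent confirmation on platelet count during daily PE (no more daily platelet measurements". The subject gets time x, non-responder, censored. Footnote c says there is no confirmation "since daily PE has been stopped by Investigator for clinical response which does not meet protocol definition of response".
- **Blinding.** Protocol 7.5: "The Investigator will be informed of the treatment at the time of randomisation".
- **Sensitivity analysis.** SAP Table 2 turns case 5 into an event at x. In the same step it makes an event of case 6: "No recovery of platelets, however daily PE stopped (daily PE considered surrogate for response".

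**The concern.** Protocol 4.3 and 7.1 tie the end of daily PE to platelet normalisation, among other criteria, and do not recommend tapering. A stop close to first recovery is therefore foreseeable, and case 5 shows that the SAP expects it. That stop also ends the daily sampling the endpoint needs.

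The log-rank test and Kaplan-Meier estimates assume that censoring is unrelated to the event. In case 5 the subject leaves the risk set at the moment platelets recover, through a decision by someone who knows the arm. Equal shares in both arms cost events and lengthen the estimated medians. Unequal shares bias the hazard ratio, in either direction. This is a stated rule of the primary analysis.

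**Working it through.** **1. Where the gap lies.** Let x be the day of first recovery, so that the 48-hour point is x+2. Weeks are counted here from the day-1 visit (the first day after daily PE).

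| Last daily PE | Day-1 visit | Scheduled pair at x+2? | Next weekly window |
|---|---|---|---|
| x−1 | x | no | x+5 to x+9 |
| x | x+1 | no | x+6 to x+10 |
| x+1 | x+2 | yes (day-1 visit) | not needed |
| x+2 or later | x+3 or later | yes (daily sample) | not needed |

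The anchor for the weekly visits is not stated. Counting from the last daily PE moves each window one day earlier, and still none reaches x+2.

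**2. The plan's own figure.** Inputs from Protocol 10.4 and SAP 6.1.4: medians 6 and 3.36 days, HR 6/3.36 = 1.786, one-sided 2.5%, power 80%, 1:1 allocation, 15% loss.

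- Events: 4 × (1.960 + 0.842)² / (ln 1.786)² = 93.4.
- Sample size: 93.4/0.85 = 110. This matches the plan.
- Check: d = 110 × 0.85 = 93.5, and power = Φ(√(93.5/4) × ln 1.786 − 1.96) = 0.80.

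**3. Model for case 5.** The documents give no case-5 share, so every share below is assumed, and every case-5 subject is taken as a true responder. If a share f of responders in an arm is censored at recovery, the hazard of counted events in that arm is multiplied by (1−f). So is its number of events, starting from 93.5/2 = 46.75. The Kaplan-Meier median is divided by (1−f).

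The simulation used 20,000 runs, 47 per arm, exponential times, a day-30 cut-off and an unstratified one-sided log-rank test at 0.025.

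**4. Equal shares.** d = 93.5 × (1−f), HR unchanged.

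| f | d | Power, formula | Power, simulation |
|---|---|---|---|
| 0 | 93.5 | 0.800 | 0.785 |
| 10% | 84.2 | 0.758 | 0.742 |
| 20% | 74.8 | 0.708 | 0.686 |
| 30% | 65.5 | 0.650 | 0.625 |

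Simulated type I error stays at 0.024 to 0.028. At 20% the medians become 6/0.8 = 7.5 and 3.36/0.8 = 4.2 days.

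**5. Unequal shares, true HR 1.786.** Observed HR = 1.786 × (1−f_ALX)/(1−f_control).

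- 10% control, 20% ALX-0081: d = 46.75 × (0.9 + 0.8) = 79.5; HR = 1.786 × 0.8/0.9 = 1.588; power 0.540 (simulation 0.516).
- 5% control, 10% ALX-0081: d = 86.5; power 0.686 (simulation 0.654).

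**6. Unequal shares, no true effect.** Error = 1 − Φ(1.96 − √(d/4) × ln[(1−f_ALX)/(1−f_control)]).

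- 20% control, 10% ALX-0081: d = 79.5; √(79.5/4) × ln(0.9/0.8) = 0.525; error = 1 − Φ(1.435) = 0.076 (simulation 0.079).
- 10% control, 5% ALX-0081: error 0.044 (simulation 0.045).

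**7. Alternative codings at 20% control, 10% ALX-0081, simulated.**

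- Case 5 as an event, as in Table 2 but with no case-6 subjects present: error 0.026, power 0.790.
- Case 5 as an event only if a later pair meets the criteria: error 0.027, 0.033 or 0.045 when 100, 80 or 50% of case-5 subjects meet them.

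**The case against.** The strongest reply is that the SAP has already seen the scenario, named it and pre-specified an analysis that reverses it. With no case-6 subjects, Table 2 restores the error to 0.026, and a case-5-only analysis does no better on that measure. But real data may contain case-6 subjects, and Table 2 makes them events in the same step. A difference between the Table 1 and Table 2 results could then not be attributed to either change. Table 2 also accepts case 5 without any later check.

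Second, the endpoint wording requires the 48-hour measure, and an unscheduled visit can supply it. The PK/vWF/FVIII draw 18–24 hours after study drug on the first day after daily PE also falls near x+2 when the last daily PE is on x. This stands as a reason why the share may be small. It does not close the gap: that draw goes to the central laboratory and includes neither platelets nor LDH, and confirmation still depends on initiative at unblinded sites.

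Third, a last PE on x−1 might be read as case 6. Case 6 requires no recovery, however. Counts are taken before PE, so withholding PE on the day the count recovers makes x−1 the last daily PE with recovery seen, which fits case 5.

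Fourth, the shares are assumed. This stands in full. At a 5% share in both arms simulated power is 0.76; at 5% control and 3% ALX-0081 the error is 0.034. If case 5 used up the 15% loss allowance instead of adding to it, an equal 15% share would leave d = 110 × 0.85 = 93.5 and formula power at 0.80.

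**Conclusion.** The concern holds. The schedule leaves no platelet/LDH pair at 48 hours in exactly two positions, a last daily PE on x or on x−1. Unless the site adds a sample, case 5 then censors the subject at recovery. The censoring is informative by construction. Whether it differs by arm cannot be known from the documents; the open-label investigator makes that possible, not certain.

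The size is illustrative. It rests on assumed shares, exponential times and every case-5 subject being a true responder. Equal shares cost about 4 to 15 points of power over the 10–30% range. A difference of 10 points between arms can take power to about 0.54 or the one-sided error to about 0.08. The sample size of 110 reproduces and is not in dispute. The point should be addressed before database lock; it does not call for a new primary analysis.

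**What to change.** 1. **Protocol Table 11.** Add a local platelet and LDH draw at 48 hours, with a stated window, after the first count of at least 150,000/µL whenever daily PE has stopped. This does not touch when PE is stopped. For subjects already past that point, use any local result inside the window, scheduled or not.
2. **SAP 6.3.1.** Add a sensitivity analysis that changes case 5 only. Count the response at x if the first platelet/LDH pair at or after 48 hours (in practice the first weekly sample) meets the criteria with no re-initiation of PE in between. Otherwise keep the Table 1 coding. Report the number of case-5 subjects by arm.
3. **Keep the primary coding of cases 5 and 6.** In particular, do not hold unconfirmed subjects at risk to day 30. In simulation that lowers power to 0.651 at an equal 2% share (0.775 under the current rule) and 0.368 at 10% (0.742). It raises the error to 0.194 at 20% control and 10% ALX-0081 (0.079).

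The cost is SAP wording and one extra local draw in some subjects. They stay in hospital at least one day after the last daily PE (Protocol 4.4) and are then injected daily by medical or paramedical personnel (Protocol 7.2).

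There are two limits. Item 1 cannot help subjects already past 48 hours, who may be many: SAP 6.1.4 and 6.1.5 show that accrual had overrun 1.5 years and that data had been seen. Item 2 accepts some confirmations later than 48 hours, so it brings some durability of response into the analysis.

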### *Sensitivity analyses with regards to primary (and secondary) efficacy endpoints*

Sensitivity analyses comprise the following aspects:

- 1) For efficacy endpoints (EPs) (primary and secondary), analyses performed on per protocol (PP) populations. Details on major deviations are specified in [Appendix II](#).
- 2) Analysis of treatment effect adjusted for the following covariates:
  - a. ADAMTS13 activity at baseline: < 5% vs.  $\geq$  5%,
  - b. von Willebrand Factor (vWF) level (continuous),
  - c. first episode vs. recurrent disease (as described in [Section 6.2.4](#)),
  - d. Ristocetin Cofactor (RICO) suppression < 20% throughout treatment period: yes vs. no,
  - e. absence/presence of one PE session prior to randomisation.

A Cox proportional hazards model is fit to the data, and in addition to treatment, significant (5% significance level; SL) covariates are retained. This will be represented by means of Forest plots for the covariates found to be significant.

- 3) Analysis of non-confirmed and confirmed platelet response (instead of confirmed platelet response only) for the ITT population: see **Table 2**, with changes to
- 4) **Table 1** indicated in **bold green**.
- 5) Assessment of impact (potential bias) of use of rituximab during daily PE: log rank analysis of primary endpoint with subjects censored at time they start using rituximab for the ITT population. Use of rituximab will be determined by using the Concomitant Medications data (both PE related and not PE related) with ATC code “L01XC” (coded term “RITUXIMAB”).

**Table 2: Censoring/event scenarios (for ITT and PP analysis of non-confirmed and confirmed platelet response; changes to Table 1 indicated in bold green)**

Case	Description	Time at risk/ Time to recovery of platelets (days)	Responder	Censored (No = 0; Yes = 1)
1	No event in 30 days of continuous daily PE a	30	No	1
2	At day 30, confirmed recovery of platelets (per protocol)	30	Yes	0
3	At day x b (1 st measurement of platelet recovery), confirmed recovery of platelets, ideal case (per protocol)	x	Yes	0
4	No event occurred and subject is no longer in trial at day x b (including replaced subjects who are dosed)	x	No	1
5	At day xb (1st measurement of platelet recovery), subject has recovery of platelets, however, missing data at 48 hours later, and no subsequent confirmation on platelet count during daily PE (no more daily platelet measurements)c	x	Yes	0
6	No recovery of platelets, however daily PE stopped (daily PE considered surrogate for responsed). Except if PE stopped due to AEe (then idem case 4)	Time of last daily PE	Yes	0
7	Subject not dosed (after randomisation)	1	No	1

a PE = plasma exchange.

b At day x within 30 days assessment period.

c No subsequent confirmation during daily PE, since daily PE has been stopped by Investigator for clinical response which does not meet protocol definition of response.

d Certain subject's platelet counts 'hover' around 150,000/ $\mu$ L and in clinical practice PE is stopped.

e Start and stop dates of adverse events related to PE will need to be compared to PE stop dates in order to identify PE stopped due to AE.

